3.2 Exclusion Criteria

- 3.2.1 Patients who have previously been treated with brain irradiation to the region that would result in overlap of the radiation fields.

- 3.2.2 Tumor foci detected below the tentorium.
- 3.2.3 Multifocal disease or leptomeningeal spread.
- 3.2.4 Prior allergic reaction to the study drugs involved in this protocol.
- 3.2.5 Inability to have neither an MRI nor a CT scan. Patients with a pacemaker must undergo CT instead of MRI to be eligible.
- 3.2.6 Pediatric patients (age <18), pregnant women, and nursing patients will be excluded.

3.3 **Informed Consent Process**

Patients who meet the inclusion and exclusion criteria who are seen in the neuro-oncology, neurosurgery, or radiation oncology clinic will be identified for recruitment. Patients will be evaluated by a multi-disciplinary team composed of radiation oncologists, neurosurgeons, and neuro-oncologists. During their visit, either a physician or a research coordinator will explain the study to the patient. They will be given the informed consent form to read. If they agree to participate, they will be asked to sign the consent form prior to participating.

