9.1.2 Disease Parameters

Local tumor progression is defined as the radiographic appearance of a new or increasing enhancing lesion within the radiosurgical target volume. Patients with increased tumor size on MRI may continue on the protocol until true tumor progression (i.e., not pseudo-progression) is determined by the treating physicians.

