9.1.3 Methods for Evaluation of Measurable Disease

9.1.4 Response Criteria

The primary measure of response will be by serial measures of the product of the two largest cross-sectional diameters. Response will also be evaluated in this study using the [following](#) criteria:

9.1.4.1 Complete response (CR): Circumstance when the enhancing tumor is no longer seen by neuroimaging.

9.1.4.2 Partial response (PR): Decrease of >50% in the product of the two greatest diameters on the follow-up MRI scan. No new lesions may appear. The dose of dexamethasone must be the same or lower than at baseline.

9.1.4.3 Minor response (MR): Decrease of <50% in the product of the two greatest diameters on the follow-up MRI scan. Neither partial response or progressive disease.

9.1.4.4 Progression (P): A >25% increase in tumor area (product of the two greatest diameters) provided that the patient has not has a decrease in steroid dose since the last evaluation period. A concomitant decrease in steroid dose will rule out a progression designation during the first 2 months after the completion of XRT.

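### The Progression category has no new-lesion criterion, so a new enhancing lesion outside the target can be filed as a minor response, be read as a complete response, or have no category

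*Combined protocol and SAP*

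**What the plan says.** All references are to the combined protocol and SAP.

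- **Progression (9.1.4.4; repeated in the Appendix B follow-up form):** "A >25% increase in tumor area (product of the two greatest diameters) provided that the patient has not has a decrease in steroid dose". There is no new-lesion clause and no clause on location.
- **Complete response (9.1.4.1):** "Circumstance when the enhancing tumor is no longer seen by neuroimaging". New lesions are not mentioned.
- **Partial response (9.1.4.2):** a fall of more than 50% in the product of diameters, with the condition "No new lesions may appear" and a steroid condition.
- **Minor response (9.1.4.3):** a fall of less than 50%, and "Neither partial response or progressive disease".
- **Local progression (9.1.2):** "the radiographic appearance of a new or increasing enhancing lesion within the radiosurgical target volume". For increased tumor size on MRI, patients may stay on protocol "until true tumor progression (i.e., not pseudo-progression) is determined by the treating physicians".
- **Entry (3.2.3):** "Multifocal disease or leptomeningeal spread" is an exclusion.
- **Objectives and endpoints:** the synopsis, objective 1.2.4 and Section 9.2.4 call for patterns of failure or recurrence without restriction. Section 11.1.2 limits this to local recurrence. Progression-free survival appears in Section 9.2.2 with no event definition.
- **Follow-up form:** it measures the protocol lesion, offers four boxes (complete, partial and minor response, progression) and has a free-text comments area. It has no field for a new lesion or for the site of failure.

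**The concern.** Multifocal disease is excluded at entry, so a separate enhancing focus at follow-up is new since entry. The criteria recognise that it matters, because it rules out a partial response, but they never say what the patient then is. The category that should receive the patient depends on area alone.

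This matters because of how the target is drawn. Under Section 4.3 the CTV is the GTV plus 0.5 cm, reducible to 0 mm at anatomic borders. T2 and FLAIR signal are deliberately left out, and the PTV adds no further margin. Whether failures arise inside or outside that tight volume is the question a patterns-of-failure analysis has to answer here. If an out-of-target first failure can be filed as a response, or left without a category, the response table and any progression date built on it can be wrong for that patient. The maximum stated in Section 11.2.1 is 15 patients per arm, so one misfiled patient is at least 1/15 = 6.7 percentage points of an arm-level rate.

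**Working it through.** The plan gives no figure to reproduce. The check applies the written rules to example patients.

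**Assumptions (illustrative, not from the documents).** Baseline product 40 × 30 = 1200 mm²; a new enhancing lesion lies wholly outside the target; no steroid change; comparison is with baseline.

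**Formula.** Change = (follow-up product − 1200) / 1200. The last column adds the new lesion's area to the follow-up product, in case tumor area is read as total area.

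| Index lesion now (mm²) | New lesion (mm²) | Change, index lesion | Category on the index lesion | Change if areas are summed |
|---|---|---|---|---|
| 0 | 15 × 10 = 150 | −100% | Complete response, if the enhancing tumor means the index lesion | (0 + 150 − 1200)/1200 = −87.5% |
| 25 × 20 = 500 | 150 | −58.3% | None: partial response barred, fall not under 50%, no increase | (500 + 150 − 1200)/1200 = −45.8% |
| 36 × 28 = 1008 | 20 × 15 = 300 | −16% | Minor response | (1008 + 300 − 1200)/1200 = +9% |
| 1008 | 25 × 20 = 500 | −16% | Minor response | (1008 + 500 − 1200)/1200 = +25.7% |

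**Reading the table.**

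1. No case is progression on the protocol lesion, which is the only lesion the form measures.
2. Summing areas would make the last case progression but not the third. The outcome would then depend on the new lesion's size relative to the index lesion, and no text says that areas are to be summed.
3. The minor-response definition excludes progressive disease. The only criterion that Section 9.1.4 gives for progressive disease is the >25% rule, so the exclusion does not catch rows three and four. A reader who excluded them by judgement would be left with no box to tick.
4. In none of the cases does the new lesion meet the Section 9.1.2 definition, because it lies outside the target.

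**Failure site.** Section 9.1.2 supplies a boundary: enhancement within the target is local. No definition names the complement, the form does not capture it, and Section 11.1.2 as worded does not ask for it, although objective 1.2.4 does.

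**The case against.** The case on the other side has real force on several points.

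- **The local definition is correct.** A reader might infer that Section 9.1.2 is faulty because it stops at the target. It is not: a definition of local progression should stop there, and it already provides the inside/outside line. What is missing is a named counterpart.
- **Response is still measured.** Section 9.1.4 makes the serial product of diameters the primary measure and the categories an additional one. A patient without a category still has that measure. Only the categorical rates are exposed.
- **Gross total resection is partly covered.** A reader might infer that recurrence from a zero baseline cannot be defined. Section 9.1.2 has no percentage threshold and the target includes the cavity, so in-target recurrence can be identified.
- **Failures need not be lost.** The scans, outside source documents, treatment plan and free-text comments would let someone reconstruct the site later. The documents support misclassification under the stated rule, not irrecoverable loss.
- **Physicians decide on true progression.** They may well call a new lesion progression. But that sentence in Section 9.1.2 concerns increased tumor size and pseudo-progression and gives no new-lesion criterion. Disease progression in Sections 4.8 and 9.1 is broad enough to include such a lesion, but it is undefined.
- **The stakes are secondary.** This is a 3 + 3 dose-finding study, and progression-free survival is absent from the objectives and from Section 11.

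The first three points and the last stand and limit the finding. The fourth softens it. The fifth does not answer it, because an unwritten judgement cannot give consistent categories.

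**Conclusion.** The point holds. The written progression rule gives a wrong category, or none, to a patient with a new enhancing lesion outside the target, unless the index lesion has itself grown by more than 25%. This is a stated rule producing a wrong result, not merely a missing detail, and it should be corrected.

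Its reach is limited to categorical response, patterns of failure and progression-free survival. The last assumes that category P dates the event, which the plan does not say. The serial product measure is unaffected, and so is the DLT/MTD endpoint. A reader might infer that a sizeable share of patients would be misfiled or that progression-free survival is materially biased; the documents contain nothing from which either can be computed. The result rests on a literal reading in which the index lesion alone is assessed, as the form does.

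**What to change.** For endpoint analysis only:

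1. In Section 9.1.4.4 and on the form, define progression as the existing >25% area increase **or** a new enhancing lesion anywhere in the brain. State that a new lesion also bars complete and minor response, and that the physician determination of true versus pseudo-progression in Section 9.1.2 extends to new lesions.
2. Add two form fields: new lesion (yes/no) and first-failure site, using the existing Section 9.1.2 boundary. Local means any new or increasing enhancement within the target volume; non-local means enhancement with no overlap with it; both means both are present. A marginal subcategory is optional but must be consistent with Section 9.1.2: a lesion crossing the target edge already counts as local there.
3. Align Section 11.1.2 with objective 1.2.4.

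Whether the definition also governs removal from study (4.8) and the imaging schedule (9.1) is for the sponsor to state.

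**Cost.** The same MRIs are used, but site assignment requires comparison with the treatment plan, and the form's assessment text must be reworded. Some patients now filed as minor response become progression, progression-free survival may be somewhat shorter, and some treatment effect may be counted as progression.

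**Side notes, not part of this finding.** The >25% rule names no reference scan. Changes from 0 to +25% have no category. Start date and censoring for progression-free survival are not given. One steroid sentence in Section 9.1.4.4 has no time limit while the other reads "A concomitant decrease in steroid dose will rule out a progression designation during the first 2 months after the completion of XRT"; the sponsor should reconcile them.

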9.2 Other Response Parameters

9.2.1 Acute and late side effects will be assessed.

Common Terminology Criteria for Adverse Events (CTCAE) v4.0 will be used to grade adverse events. Acute toxicity is defined as occurring within 30 days of radiotherapy. Late toxicity is defined as occurring more than 30 days following the radiotherapy treatment.

9.2.2 The progression-free survival rate will be determined.

9.2.3 The overall survival rate will be determined.

9.2.4 The patterns of tumor recurrence will be determined.

9.2.5 The Health Related Quality of Life (HRQOL) will be measured used the validated EORTC QLQ-C30 general and BN-20 brain tumor specific scales as well as the M.D. Anderson Symptom Inventory –Brain Tumor (MDASI-BT)

For those subjects unable to appear in person for clinic visits, HRQOL questionnaires will be completed via a telephone interview or mail.

10. DATA REPORTING / REGULATORY CONSIDERATIONS

10.1 Monitoring plan

Stanford Cancer Center (SCC) Data and Safety Monitoring Committee (DSMC) will be responsible for monitoring the research yearly and will operate independently from the clinical investigators. The primary responsibility of the DSMC is to review the reported study data to confirm it is accurate, complete, and verifiable from source documents. The DSMC will also confirm that the conduct of the trial maintains the safety and well being of human subjects, and is in compliance with the currently approved protocol, with GCP, and with applicable regulatory requirements. Study

safety data will be reviewed by the DSMC in the form of summary reports or data listings on a regular basis.

10.2 Stopping rules (for the individual patient and for the study as a whole)

Dose escalation will follow a traditional 3 + 3 design.

Number of Patients with DLT at a Given Dose Level	Escalation Decision Rule
0 out of 3	Enter 3 patients at the next dose level.
1 out of 3	Enter at least 3 more patients at the current dose level. 
• If 0 of these 3 experiences a DLT (i.e., 1 out of 6), then proceed to next dose level.• If 1 or more of these 6 experiences a DLT (2 or more out of 6), then dose escalation will be stopped. Three additional patients will be entered at the next lower dose level if only 3 patients were previously entered.
>1 out of 3	Dose escalation will be stopped. Three additional patients will be entered at the next lower dose level if only 3 patients were previously entered.

Should a patient not be evaluable at 30 days (due to death unrelated to protocol treatment or loss to follow-up or discontinuation of the protocol follow-up per patient preference), then additional patients may be enrolled on each arm such that at least 3 are evaluable for DLT.

The occurrence of late toxicities will be continuously monitored. If a late DLT occurs in 2 patients at a certain dose level after the radiation dose had already been escalated to the next level, the MTD will be backtracked to the level below the one at which the DLTs occurred.

10.3 Confidentiality

All signed informed consents and data files (contains patients' names, medical record numbers, treatment, and follow-up information) for this study will be kept in a secure office in the department of Neurosurgery and Radiation Oncology. The electronic data file for this study, which contains patients' names, medical record numbers, treatment, and follow-up information, is kept under password protection.

11. STATISTICAL CONSIDERATIONS

11.1 Endpoints

11.1.1 Phase I Primary endpoint

The MTD and DLT of hypofractionated radiotherapy with temozolomide will be determined.

11.1.2 Secondary endpoints

The short- and long-term adverse effects will be determined. The overall survival rate will be calculated. Radiographic response rates and patterns of local tumor recurrence will be determined. Health related quality of life will be assessed.

11.2 Sample Size

11.2.1 Accrual estimates

Three patients minimum enrolled per dose level, plus 3 additional at the dose level of the MTD. The maximum number of patients needed for the phase I study will depend on the number of dose levels reached. If all four dose levels are reached, the maximum number of patients will be 15 per arm.

REFERENCES

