TITLE	A Phase I/II Trial Of Temozolomide And Hypofractionated Radiotherapy In The Treatment Of Supratentorial Glioblastoma Multiforme
STUDY PHASE	I/II
INDICATION	Newly diagnosed, histologically confirmed supratentorial GBM.
PRIMARY OBJECTIVES	Phase I - Primary Objective Determine the maximum tolerated dose (MTD) of hypofractionated radiotherapy given in 5 fractions with temozolomide for the treatment of glioblastoma multiforme.
SECONDARY OBJECTIVES	Determine the short- and long-term adverse effects. Determine the radiographic response rate. Determine the overall survival rate. Perform patterns of failure analysis. Assess quality of life during treatment.
HYPOTHESES	Five fraction stereotactic radiosurgery (SRS) with concurrent temozolomide will be well-tolerated; the duration of radiotherapy can safely be shortened to 5 treatments without compromising the local control or overall survival rates.
STUDY DESIGN	Phase I: The MTD for five-fraction SRS concurrent with temozolomide will be determined using a 3+3 study design.
PRIMARY ENDPOINTS AND SECONDARY ENDPOINTS	Phase I Primary endpoint The MTD and DLT of hypofractionated radiotherapy with temozolomide will be determined. Secondary endpoints The short- and long-term adverse effects will be determined. The overall survival rate will be calculated. Patterns of failure analysis will be performed. Health related quality of life will be measured.
SAMPLE SIZE BY TREATMENT GROUP	Three patients will be enrolled per dose level per arm. The maximum number of patients

	needed for the phase I study will depend on the number of dose levels reached. If all 4 dose levels are reached, the maximum number of patients will be 15 per arm.

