4.3 Radiation Therapy

1.1.1. Dose specifications/escalation

Radiation will be delivered in five fractions. Provided that the MTD has not been reached, the total dose will be increased as follows:

Dose Level	Dose Per Fraction (Gy)	Total Dose (Gy)
1	5	25
2	6	30
3	7	35
4	8	40

There will be 2 arms to this study:

Arm	PTV volume (cm ³)
1	< 60
2	60-150

A minimum observation period of 30 days following radiotherapy is required prior to proceeding with the next higher dose level.

Common Terminology Criteria for Adverse Events (CTCAE) v4.0 will be used to grade adverse events:

(<http://evs.nci.nih.gov/ftp1/CTCAE/About.html>)

A dose limiting toxicity (DLT) is defined as a treatment related grade 3 - 5 CNS toxicity. Acute toxicity is defined as occurring within <30 days of the end of

radiotherapy. Late toxicity is defined as occurring ≥ 30 days of the end of radiotherapy. The highest dose achieved with an acceptable level of toxicity will be considered the MTD. The highest dose level allowed in this study is 40 Gy. The occurrence of late toxicities will be continuously monitored. If a late DLT occurs in 2 patients at a certain dose level after the radiation dose had already been escalated to the next level, the MTD will be backtracked to the level below the one at which the DLTs occurred.

Dose escalation will follow a traditional 3 + 3 design:

Number of Patients with DLT at a Given Dose Level	Escalation Decision Rule
0 out of 3	Enter 3 patients at the next dose level.
1 out of 3	Enter at least 3 more patients at the current dose level. 
 • If 0 of these 3 experiences a DLT (i.e., 1 out of 6), then proceed to next dose level. • If 1 or more of these 6 experiences a DLT (2 or more out of 6), then dose escalation will be stopped. Three additional patients will be entered at the next lower dose level if only 3 patients were previously entered.
>1 out of 3	Dose escalation will be stopped. Three additional patients will be entered at the next lower dose level if only 3 patients were previously entered.

Should a patient not be evaluable at 30 days (due to death unrelated to protocol treatment or loss to follow-up or discontinuation of the protocol follow-up per patient preference), then additional patients may be enrolled on each arm such that at least 3 are evaluable for DLT.

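### Fifteen patients per arm is called the maximum if all four dose levels are reached, but the protocol's own 3+3 table can require 18, 21 or 24

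*Combined protocol and SAP*

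**What the plan says.** The sample size appears in two places. Section 11.2.1 gives the basis, "Three patients minimum enrolled per dose level, plus 3 additional at the dose level of the MTD", and then the total: "If all four dose levels are reached, the maximum number of patients will be 15 per arm". The synopsis row on sample size gives a different per-level count, "Three patients will be enrolled per dose level per arm", with no addition at the MTD, and the same total: "If all 4 dose levels are reached, the maximum number of patients will be 15 per arm".

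The rules that decide how many patients are entered are in the escalation table, printed in section 4.3 (dose specifications/escalation) and again in section 10.2. After 0 of 3 DLTs, three patients go to the next level. After 1 of 3, the instruction is "Enter at least 3 more patients at the current dose level", followed by "If 0 of these 3 experiences a DLT (i.e., 1 out of 6), then proceed to next dose level". After a stop, "Three additional patients will be entered at the next lower dose level if only 3 patients were previously entered". For patients who cannot be evaluated at 30 days, "additional patients may be enrolled on each arm such that at least 3 are evaluable for DLT".

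There are four dose levels and two arms, defined by PTV volume. Each arm has its own total.

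**The concern.** The total and the table count different things. The total counts one expansion, at the MTD. The table expands any level that shows 1 of 3 and then moves up if no further DLT occurs, so an expanded level need not be the MTD. Nothing in the protocol restricts expansion to one level.

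Fifteen per arm is the only total the protocol offers. On some paths an arm that follows the table correctly will pass the stated maximum, possibly while a cohort at level 4 or a step-down cohort still has to be filled. The table and the maximum cannot then both be honoured. Nothing makes 15 a stop to enrolment, so the likely consequence on those paths is an accrual ceiling exceeded mid-trial, not a different MTD.

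Two smaller mismatches belong to the same point. The synopsis count of three per level gives 4 × 3 = 12, not 15. And 11.2.1 adds three patients at the MTD, while the table does not say whether anyone is added when level 4 shows 0 of 3, so it is unclear whether an arm with no DLTs ends at 12 or 15.

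**Working it through.** **Inputs.** Four levels, two arms, cohorts of 3 and the escalation rules (section 4.3, repeated in 10.2); 3 per level plus 3 at the MTD (11.2.1). The documents give no DLT rate.

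**The plan's figure.** 4 × 3 + 3 = 15. It reproduces, and it corresponds to exactly one level holding 6 patients.

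**Totals the table allows.** If each expansion is exactly 3 and level 4 is reached, N = 12 + 3k, where k is the number of levels holding 6:

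| k | N per arm | Example (levels 1 to 4) |
|---|---|---|
| 0 | 12 | 3, 3, 3, 3 (only if none are added at a cleared level 4) |
| 1 | 15 | 3, 3, 3, 6 |
| 2 | 18 | 6, 3, 3, 6 |
| 3 | 21 | 3, 6, 6, 6 |
| 4 | 24 | 6, 6, 6, 6 |

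The case of 18 needs only the table: 1 of 6 at level 1, 0 of 3 at levels 2 and 3, then 1 of 3 at level 4, which calls for three more. A second route is 0 of 3 at levels 1 to 3, 1 of 3 at level 4, a further DLT in the expansion, then three more at level 3: 3 + 3 + 6 + 6 = 18. The case of 24 is 1 of 6 at levels 1 to 3 and 1 of 3 at level 4. Over both arms that is 2 × 24 = 48, against 2 × 15 = 30.

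If the MTD addition in 11.2.1 is a top-up to 6, k is at least 1 once level 4 is reached, so 15 is then the minimum. Not every lower-level expansion exceeds 15: 6 + 6 + 3 with level 2 as the MTD is exactly 15. Conversely, an arm that never reaches level 4 can use 6 + 6 + 6 = 18.

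**How often.** Every path through the table was enumerated exactly, with binomial probabilities at assumed DLT rates, expansions of 3, and stopping at 2 or more of 6. The ranges cover one step down or repeated steps down after a stop, and whether DLTs among the patients added at level 4 trigger a step down.

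| Assumed DLT rate | P(N > 15), 3 added at a cleared level 4 | P(N > 15), none added |
|---|---|---|
| 5% at every level | 0.306–0.310 | 0.087 |
| 10% at every level | 0.390–0.399 | 0.184–0.186 |
| 20% at every level | 0.268–0.281 | 0.188–0.195 |
| 5/10/15/20% by level | 0.406–0.431 | 0.268–0.273 |

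These are unconditional chances for one arm. Across the same scenarios:

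- P(N > 18): 0.039–0.100 with the addition, 0.010–0.060 without.
- P(N = 24): 0.0018–0.0132 with, 0.0004–0.0079 without.
- Expected N: 12.19–15.86 with, 11.65–14.67 without.

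**Given that level 4 is reached**, which is the condition in the protocol's sentence, P(N > 15) at flat rates of 5%, 10% and 20% is 33%, 52% and 70% with the addition, and 9%, 23% and 46% without.

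**Hand check at 10%, with the addition and repeated steps down.**

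- A level is cleared by 0 of 3, or by 1 of 3 then 0 of 3: 0.729 + 0.243 × 0.729 = 0.906. Level 4 is reached with probability 0.906147³ = 0.744.
- Exactly 15 with level 4 reached arises in three ways.
  - Levels 1 to 3 clear at 0 of 3 and level 4 has at most 1 of 6: 0.729³ × 0.8857 = 0.3432.
  - Levels 1 to 3 clear at 0 of 3, level 4 has 2 or more of 3, and the three added at level 3 have at most one DLT: 0.729³ × 0.028 × 0.972 = 0.0105.
  - Level 3 clears at 1 of 6 and level 4 has 2 or more of 3: 0.729² × 0.1771 × 0.028 = 0.0026.
- The sum is 0.3563, and 1 − 0.3563/0.744 = 0.521, in agreement with the 52% above.

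**The case against.** The strongest reply is that the figure is administrative. It sits under a heading about accrual estimates, beside a sentence that speaks of a minimum per level. No decision rule, endpoint or power calculation uses it, and the table chooses the next cohort without reference to it. That is correct, and it limits the consequence to accrual planning. It does not rescue the statement, because both places say maximum and the table contradicts that.

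A second reply is that large totals are unlikely. For 24 this is true. For exceeding 15 it is not: the unconditional chance is below one half in every scenario, but it is 9% or more throughout. Once level 4 is reached it passes one half at flat rates of 10% and 20% if the MTD addition applies. All these rates are assumptions. The reachable totals do not depend on them.

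Three cautions stand:

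- Because the table sets a lower bound on the expansion and replacements are not capped, 24 is itself an upper figure only for evaluable patients in expansions of exactly 3.
- The table's stopping line refers to 1 or more of 6 while its parenthesis says 2 or more. The calculations use 2 or more, which fits the instruction to proceed on 1 of 6. The second route to 18 holds under either reading.
- The synopsis line on three per level can be read as a cohort size, so taken alone it is a matter of clarity.

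**Conclusion.** The concern holds. Fifteen per arm is the total when one level is expanded. It is not the maximum when all four levels are reached: 18, 21 and 24 are all possible under the protocol's table. The upper figure is 24 evaluable patients per arm (48 against 30 over both arms), assuming expansions of exactly 3 and an MTD addition that tops the level up to 6, before replacements. That 15 can be exceeded needs neither of these assumptions nor any DLT rate.

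The chance that one arm exceeds 15 is 27–43% with three patients added at a cleared level 4 and 9–27% without, over the assumed rates. The MTD rule is not affected. What is wrong is the protocol's only stated sample size, and it should be corrected.

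**What to change.** In the synopsis and in 11.2.1, replace the sentence giving the maximum with wording such as: *An arm that reaches level 4 needs 15 evaluable patients if no level other than the MTD level is expanded, and up to 24 (48 over both arms) if every level is expanded to 6. Replacements for non-evaluable patients are additional.* State the two assumptions behind 24 next to it: expansions of 3, and an MTD addition that tops the level up to 6. Make the synopsis count per level agree with 11.2.1.

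Reconcile 11.2.1 with the table in 4.3 and 10.2, so that all three say the same about whether patients are added at the top level after 0 of 3. The 15 in the wording above follows 11.2.1. If the sponsor settles that point otherwise, the lower figure for an arm with no expansion is 12.

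The cost is a few sentences in the synopsis and 11.2.1, and one clarifying row in the table. The handling of DLTs at levels 1 to 3 does not change. The stated accrual ceiling rises, so accrual planning should be revised to match.

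### The stated maximum of 15 patients per arm is the smallest total if all four dose levels are reached; the plan's own 3+3 rules allow up to 24

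*Combined protocol and SAP*

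**What the plan says.** Section 11.2.1 (Accrual estimates) builds the sample size from a per-level minimum: "Three patients minimum enrolled per dose level, plus 3 additional at the dose level of the MTD". It then gives the ceiling: "If all four dose levels are reached, the maximum number of patients will be 15 per arm". The synopsis, under sample size by treatment group, repeats it: "If all 4 dose levels are reached, the maximum number of patients will be 15 per arm".

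The escalation table in 4.3 (Dose specifications/escalation), reproduced in 10.2 (Stopping rules), sets how many patients are actually entered:

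- After one DLT in three: "Enter at least 3 more patients at the current dose level".
- After a clean second cohort: "If 0 of these 3 experiences a DLT (i.e., 1 out of 6), then proceed to next dose level".
- After escalation stops: "Three additional patients will be entered at the next lower dose level if only 3 patients were previously entered".

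Both sections also provide for patients who cannot be evaluated at 30 days: "additional patients may be enrolled on each arm such that at least 3 are evaluable for DLT". There are four levels (25, 30, 35 and 40 Gy), two arms defined by PTV volume, and a top dose: "The highest dose level allowed in this study is 40 Gy".

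**The concern.** The sum behind 15 starts from a minimum per level and allows only one level to grow to six, yet the result is labelled a maximum. The tables allow, and after one DLT in three require, six patients at any level. The accrual sentence and the decision rules therefore cannot both be honoured on many ordinary paths.

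The MTD in each arm is the primary endpoint. If 15 is treated as the limit:

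- One expansion among the first three levels uses 6 + 3 + 3 = 12 patients. That leaves three for 40 Gy and none to take that level to six.
- Two expansions use 6 + 6 + 3 = 15 before anyone receives 40 Gy.

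The plan does not say what happens then. If the tables are followed instead, enrolment passes the figure given as the maximum.

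**Working it through.** **Inputs.** Four levels, cohorts of three and the decision rules come from the tables in 4.3 and 10.2. The three additional patients at the MTD level come from 11.2.1. The documents give no DLT rate, so rates are assumed. All patients are taken as evaluable, DLTs as independent, and the second cohort as exactly three.

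**The plan's figure.** 4 × 3 + 3 = 15. It reproduces as arithmetic.

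**Range of totals once 40 Gy is reached.**

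- Smallest: three at each level (12) plus three at the MTD level = 15. If 40 Gy shows two or more DLTs in three, 35 Gy is brought to six: 3 + 3 + 6 + 3 = 15 again.
- A path above 15 from the table rows alone: 0/3 at 25, 30 and 35 Gy; 1/3 and then at least one more DLT at 40 Gy; three more at 35 Gy. Total 3 + 3 + 6 + 6 = 18.
- Largest: 1/6 at 25, 30 and 35 Gy, then 1/3 and a second cohort at 40 Gy. Total 6 + 6 + 6 + 6 = 24.

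Enumerating every path gives totals of 15, 18, 21 or 24 only. Over two arms the range is 30 to 48.

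**How often 15 is exceeded: worked case, p = 0.05 at every level.**

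- Level passed with three patients: a = (1 − p)³ = 0.85738.
- Level passed with six: b = 3p(1 − p)²(1 − p)³ = 0.15 × 0.95⁵ = 0.11607.
- 40 Gy reached: (a + b)³ = 0.97344³ = 0.922.
- A passed level was expanded: e = b/(a + b) = 0.11923. No expansion at the first three levels: (1 − e)³ = 0.68326. Two or more: 3e²(1 − e) + e³ = 0.039.
- 1/3 and then at least one DLT at 40 Gy: 3p(1 − p)² − b = 0.13538 − 0.11607 = 0.01931. Two or more of three at 40 Gy: 3p²(1 − p) + p³ = 0.00725.
- Total of exactly 15, given 40 Gy reached: 0.68326 × (1 − 0.01931) + e(1 − e)² × 0.00725 = 0.67007 + 0.00067 = 0.6707. The second term is the path where only 35 Gy was expanded and 40 Gy fails at once.
- More than 15: 1 − 0.6707 = 0.329.

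**All assumed rates** (rising means 5/10/15/20% over the four levels):

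| | 2% | 5% | 10% | 20% | rising |
|---|---|---|---|---|---|
| P(40 Gy reached) | 98.6% | 92.2% | 74.4% | 35.6% | 71.8% |
| P(more than 15, given 40 Gy reached) | 15.8% | 32.9% | 51.0% | 67.8% | 54.7% |
| P(more than 15), from the start of an arm | 15.6% | 30.6% | 39.0% | 26.7% | 40.6% |
| P(more than 30 over both arms), from the start | 28% | 48% | 49% | 21% | 53% |
| Mean per arm, given 40 Gy reached | 15.5 | 16.1 | 16.9 | 17.8 | 17.0 |

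**Sensitivity of the second row.**

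- Those figures do not refill 35 Gy when 40 Gy shows 0/3 and then two or more DLTs in the three added patients. Refilling it, and stepping down again after two or more of six at a lower level, gives 15.8%, 33.4%, 52.1%, 70.3% and 57.9%.
- Leaving out the three added patients at 40 Gy after 0/3, the reading kindest to the plan, gives 2.0%, 9.1%, 23.3%, 45.6% and 35.5%. The range is then 12 to 24.

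**The case against.** Several points can be made for the plan.

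- *It is only an estimate.* The sentence stands under a heading about accrual estimates, 10.2 contains no accrual cap, and nothing says enrolment halts at 15. If the tables govern, the MTD is found as designed. This stands as a limit on the consequences. It does not rescue the label: both places say maximum, and the mean given 40 Gy is already above 15.
- *15 is not strictly the minimum.* By the tables alone, 0/3 at every level ends at 12. True, but the plan's 15 is itself built with the three MTD patients from 11.2.1, and without them the upper end is still 24.
- *24 is not strict either.* The tables ask for at least three more patients, with no upper bound. However, their sub-rules count DLTs out of six, which makes six the working size of an expanded level.
- *The large totals are unlikely.* DLT is limited to treatment-related grade 3–5 CNS toxicity, and the background section describes good tolerability, so low rates fit the plan's premise better than a flat 20%. At 2–5% the mean is only 15.5 to 16.1, and exactly 24 has a chance of about 0.2% or less, given 40 Gy reached. This stands: 24 is a remote extreme. But the stated limit already fails at 18.

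The documents give no approved enrolment number or resource plan, so harm to approval or budgeting cannot be shown from them.

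**Conclusion.** The concern holds: the stated maximum is wrong as written. With 11.2.1's three MTD patients and expanded cohorts of exactly six, an arm that reaches 40 Gy needs 15 to 24 evaluable patients. The understatement is at most 24 − 15 = 9 per arm, or 18 over both arms, before replacements. That range follows from the rules and needs no assumed rate. How often 15 is passed does depend on the rate: roughly one arm in six at 2% to two in three at 20%, among arms that reach 40 Gy, and less often if the three MTD patients are left out. This is an inconsistency between the accrual sentence and the decision tables. The escalation design itself is not in question. It should be corrected because, if enforced, the limit could prevent the primary endpoint from being completed.

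**What to change.** Replace the sentence in 11.2.1 and in the synopsis with:

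> If all four dose levels are reached, 15 to 24 evaluable patients per arm are needed (at most 48 over both arms). Non-evaluable patients are replaced in addition.

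Set the accrual limit at 24 evaluable patients per arm plus a stated replacement allowance, and say that an expanded level holds six evaluable patients. If 24 per arm is not feasible, state now what is done when the limit is reached before the rule is complete, for example that the MTD for that arm is reported as not determined.

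The cost is one sentence in two places and a higher accrual ceiling. No patient is added beyond those the tables already require, and at the assumed rates the mean per arm reaching 40 Gy is about 15.5 to 18, so many of the extra places would go unused.
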